8.2. Exploratory Efficacy Endpoints and Analyses

8.2.1. Clinical Outcomes

For subjects treated with cefiderocol in combination with SOC, the number and proportion of subjects in each category will be calculated for each time point (EOT, Posttreatment and EOS). Subjects will be presented by cohort and overall, for the ITT and MITT Populations. The same analysis will be performed for subjects with cefiderocol + SOC and all subjects treated with cefiderocol.

8.2.2. Microbiological Outcomes

For subjects treated with cefiderocol in combination with SOC, the number and proportion of subjects in each category will be calculated for each time point (EOT, Posttreatment and EOS). Subjects will be presented by cohort and overall, for the MITT Population. The same analysis will be performed for subjects with cefiderocol + SOC and all subjects treated with cefiderocol.

This document is confidential.

9. Pharmacokinetic Analyses

The PK concentration data will be analyzed using SAS® version 9.4 or higher. The PK concentration listings will be performed on the PK Concentration Population, and PK concentration tables will be performed on the PK Concentration Summary Population.

Additional PK analyses, including using the pooled plasma concentration data in this study and other pediatric studies and population PK analyses, will be performed using nonlinear mixed effects model approach and will be planned and reported separately by the Clinical Pharmacology & Pharmacokinetics of Shiongi & Co., Ltd. NONMEM Version 7.3 or higher will be used for the analyses.

9.1. PK Sampling Schedule

At each PK sampling time point, up to 0.4 mL of blood (but no less than 180 µL, ie, 0.18 mL) will be obtained adding up to the maximum blood sample volumes shown in Table 9-1:

Table 9-1 Total PK Blood Sample Volumes

Cohorts	Cohort 1	Cohort 2	Cohort 3	Cohort 4	Cohorts 1 and 2 Flexible Sampling	
Age	12 years to < 18 years	6 years to < 12 years	2 years to < 6 years	3 months to < 2 years	3 point-design	4 point-design
Number of samples	5 samples	5 samples	3 samples	3 samples	3 samples	4 samples
Total PK blood volume	2.0 mL	2.0 mL	1.2 mL	1.2 mL	1.2 mL	1.6 mL

Cohorts 1 and 2: total of 5 blood samples for determination of plasma cefiderocol concentrations will be collected from each subject as specified in Table 9-2 in the multiple-dose phase during 1 of the dosing intervals from the 6th to the 12th dose of cefiderocol. In the multiple-dose phase of the study in Cohort 2, if individual blood draws are needed (versus using a central line), it will be acceptable to adjust the sampling time points to a minimum of 3 or 4 samples (versus ideally 5 samples).

Cohorts 3 and 4: A total of 3 blood samples for determination of plasma cefiderocol concentrations will be collected from each subject as specified in Table 9-2 in the multiple-dose phase during 1 of the dosing intervals from the 6th to the 12th dose of cefiderocol.

The option to use an indwelling catheter to facilitate blood sampling or application of a topical anesthetic cream prior to venipuncture will be allowed.

Table 9-2 Blood Sampling Times After Start of Infusion

Cohort	Sampling Time Points (hours) After Start of Infusion				
	1	3*	3.5	5	8
Single-dose Phase					
Cohort 1	X	X	X	X	X

This document is confidential.

Cohort 2	X	X	X	X	X
Cohort 3		X		X	X
Cohort 4		X		X	X
Multiple-dose Phase					
Cohort 1	NA	NA	NA	NA	NA
Cohort 2	X	X	X	X	X
Cohort 3		X		X	X
Cohort 4		X		X	X

NA = not applicable

* Within 15 minutes prior to the end-of-infusion using a separate line or immediately after the end of infusion using the same line and with proper flushing.

If using a 3-point design, sampling times after the start of infusion are: 3, 5, and 8 hours. If using a 4-point design, sampling times after the start of infusion are: 3, 5, and 8 hours, and 1 or 3.5 hours.

For each blood sample collected, the actual sampling time will be recorded in the eCRF.

Acceptable visit windows for PK sampling time points are detailed in Section 6.4.

9.2. Plasma Pharmacokinetic Endpoint

The following PK endpoints will be evaluated:

- Plasma cefiderocol concentrations

Plasma cefiderocol concentrations will be listed and summarized by phase.

9.3. Presentation of Concentration Data

9.3.1. Handling of Missing Data or Data Below the Lower Limit of Quantification (BLQ)

Individual plasma concentrations, if deemed to be anomalous, may be excluded from the analysis at the discretion of the PK scientist. Any such exclusion will be clearly listed in the CSR along with justification for exclusion.

Missing concentration data for all subjects who are administered scheduled study treatments will be considered as noninformative missing and will not be imputed. No concentration estimates will be provided for missing sample values.

For summary of plasma concentration, the concentration BLQ will be treated as zero (0) for calculations of mean, SD, CV%, minimum, median, and maximum and treated as missing for calculations of the Geometric mean value and CV% Geometric mean.

Samples taken far outside the sampling windows may be excluded from by-time point summary statistics; this will be determined prior to database lock.

This document is confidential.

For individual concentration-time profiles, BLQ values will be replaced with:

- Zero for time-points prior to the first non-zero concentration in a linear plot.
- Zero for time-points after the first non-zero concentration in a linear plot.
- “Missing” for all BLQ values in a semi-logarithmic plot.

9.3.2. Listing and Presentation of Individual Pharmacokinetic Data

The PKC Population will be used for all individual plasma sampling collection time and concentration listings, while all summaries and graphics will be conducted using the PKCS Population. Individual plasma concentrations of cefiderocol will be presented by cohort, phase (single-dose and multiple-dose phases), infusion time (1, 2, and 3 hours), and nominal sampling time.

The following individual plots will be produced:

- Spaghetti plot linear and semi-logarithmic plasma concentration versus time plots using actual sample times (a line to connect all time points of plasma concentration) - all Individual subjects combined (1 line per subject).

9.3.3. Summary of PK Concentrations

Table summaries and graphics will be conducted using the PKCS Population. Descriptive statistics, including N, mean, SD, CV% (calculated by $SD/mean \times 100$), Geometric mean and CV% Geometric mean, median, minimum, and maximum values will be presented for plasma concentrations by cohort, phase (single-dose and multiple dose phases), infusion time (1, 2, and 3 hours), and nominal sampling time; BLQ values will be handled according to the rules described in Section 9.3.1.

The CV% Geometric mean will be calculated according to a formula:

$$CV\% \text{ Geometric mean} = [\exp(sd^2) - 1]^{1/2} \times 100$$

where sd is the standard deviation for natural log (ln)-transformed data.

The following mean plots will be produced:

- The arithmetic mean plasma concentration with SD versus time profiles will be plotted by cohort, phase (single-dose and multiple-dose phases), and infusion time (1, 2, and 3 hours) within the same figure on linear scale and semi-logarithmic scales using nominal sampling times.

This document is confidential.

10. Pharmacokinetic/Pharmacodynamics Analyses

The pharmacokinetic/pharmacodynamic analyses will be planned in a PK Analysis Plan by Shionogi.

This document is confidential.

11. Safety

The population used for safety analyses will be the Safety Population. Safety will be assessed on the basis of adverse event (AE) reports, clinical laboratory data, physical examinations, and vital signs. By-subject listings of the safety assessments will be provided for all subjects. Summaries will be presented by dose phase (single dose or multiple dose), cohort, and overall for each dose phase, unless otherwise specified.

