2. STUDY OBJECTIVES AND ENDPOINTS

Objectives	Endpoints
Primary	

 To assess the safety and tolerability of cefiderocol after single-dose administration in hospitalized paediatric subjects 3 months to < 18 years of age with suspected or confirmed aerobic Gram-negative bacterial infections To assess the PK of cefiderocol after single-dose administration of cefiderocol in hospitalized paediatric subjects 3 months to < 18 years of age with suspected or confirmed aerobic Gram-negative bacterial infections To assess the safety and tolerability of cefiderocol after multiple-dose administration in hospitalized paediatric subjects 3 months to < 12 years of age with suspected or confirmed aerobic Gram-negative bacterial infections To assess the PK of cefiderocol after multiple-dose administration in hospitalized paediatric subjects 3 months to < 12 years of age with suspected or confirmed aerobic Gram-negative bacterial infections 	
 Adverse events Vital signs Physical examinations Clinical laboratory assessments C_{max}, AUC_{0-inf}, and $t_{1/2}$ after single dose C_{max}, $AUC_{0-\tau}$, and $t_{1/2}$ after a minimum of 4 doses
Secondary	

 Multiple-dose phase only: Whenever cefiderocol is administered alone, to assess the clinical response at the Posttreatment visit (7 [\pm4] days following End of Treatment [EOT]) and at the End-of-study (EOS) visit, AND to assess the microbiological response at the Posttreatment visit (7 [\pm4] days) following EOT and EOS (if available) 	
 Clinical outcome Microbiological outcome
Exploratory	

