In the single-dose phase, cefiderocol will be administered (in addition to SOC) at any time during the SOC treatment regimen. In the multiple-dose phase, cefiderocol will be administered on Day 1 (in addition to SOC), within 72 hours of the start of potentially effective treatment with SOC antibiotics for infection. Subjects will subsequently receive cefiderocol every 8 hours (q8h) for an expected 5 to 14 days; the total duration of cefiderocol administration will be determined by the investigator based on clinical assessment of each subject’s infection status. Each dose of cefiderocol will be administered IV over 3 hours. The infusion may be shortened if this is in the best interest of the subject and if approved by the sponsor via the Request for Shortened Infusion Duration Form. The single-dose phase will include only those subjects with normal renal function or mild renal impairment. The dose of cefiderocol for the single-dose phase will be determined based on body weight only; the maximum dose to be administered is not to exceed 2000 mg. The dose for the multiple-dose phase will be determined based on both body weight and renal function; the maximum dose to be administered is not to exceed 2000 mg. The SOC administered will be selected by the investigator based on the

suspected or confirmed pathogen(s) for the infection in accordance with local standards and can be modified at any time during the subject's participation in the study at the investigator's discretion. In the multiple-dose phase, if the subject's infection is confirmed to be Gram negative only before starting treatment, monotherapy with cefiderocol may be allowed.

End-of-treatment (EOT) assessments will occur within 24 hours after administration of cefiderocol (single-dose phase) or within 24 hours after administration of the last dose of study treatment (multiple-dose phase), or at early termination. A further clinical assessment will occur at a Posttreatment visit 7 (\pm 4) days after EOT (multiple-dose phase), which is analogous to a TOC and EOS time point, if microbiological samples are available. The EOS visit will occur 28 (+ 7) days after administration of cefiderocol in the single-dose phase or 28 (+ 7) days after administration of the last dose of study treatment in the multiple-dose phase; this visit may be performed on-site or via phone call. The study schematic including a schedule of assessments is provided in [Figure 3-1](#) and [Table 3-2](#).

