4.4. Pharmacokinetic Endpoints

The following pharmacokinetic endpoints will be evaluated:

- Plasma cefiderocol concentrations

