11.5. Physical Examinations

All physical examination data will be listed by subject and summarized by cohort.

This document is confidential.

12. Changes from Analyses Planned in Protocol

There were no changes from the analyses planned in the protocol.

This document is confidential.

13. Programming Considerations

All statistical computations and construction of TLFs will be performed using SAS® for Windows Release 9.4 (SAS® Institute Inc., Cary, NC, USA).

The format of the table shells will be followed as closely as possible; however, in the course of programming and familiarization with the database, some changes may become necessary. All changes will be documented. Major changes will be documented through a formal amendment to this document.

The below programming considerations will be followed unless already specified in the above text.

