Table 14.2.1.5 Summary of Microbiological Outcome Per Baseline Gram-negative Pathogen By Time Point (MITT Population)
Table 14.2.1.6 Summary of Microbiological Outcome at Post Treatment per Baseline Pathogen and Minimum Inhibitory Concentration Values Determined by Clinical and Laboratory Standards Institute (MITT Population)
Table 14.2.2 Plasma Cefiderocol Concentration (PKCS Population)
Table 14.3.1.1 Treatment-Emergent Adverse Events – Overall Summary (Safety Population)

This document is confidential.

Table 14.3.1.2 Treatment-Emergent Adverse Events by System Organ Class and Preferred Term (Safety Population)

Table 14.3.1.3 Treatment-Emergent Adverse Events by System Organ Class, Preferred Term and Maximum Severity (Safety Population)

Table 14.3.1.4 Treatment-related Treatment-Emergent Adverse Events by System Organ Class and Preferred Term (Safety Population)

Table 14.3.1.5 Serious Treatment-Emergent Adverse Events by System Organ Class and Preferred Term (Safety Population)

Table 14.3.4.1.1 Hematology: Summary by Visit and Change From Baseline (Safety Population)

Table 14.3.4.1.2 Blood Chemistry: Summary by Visit and Change from Baseline (Safety Population)

Table 14.3.4.1.3 Urinalysis: Summary by Visit (Safety Population)

Table 14.3.4.1.4 Summary of Laboratory Tests Outside Prespecified Outlier by Visit (Safety Population)

Table 14.3.4.2 Summary of Vital Signs by Visit and Change from Baseline (Safety Population)

Table 14.3.4.3 Summary of Physical Examination by Visit (Safety Population)

This document is confidential.

16. Index of Figures

Figure 14.2.3 Mean and SD Plasma Cefiderocol Concentration Over Time by Cohort, Phase, and Infusion Time (PKCS Population)

Figure 14.3.4.1.5 Mean (Standard Deviation) Plot of Laboratory Parameters by Time Point - Hematology (Safety Population)

Figure 14.3.4.1.6 Mean (Standard Deviation) Plot of Laboratory Parameters by Time Point - Chemistry (Safety Population)

This document is confidential.

17. Index of Listings

Listing 16.2.1.1 Subject Disposition (All Subjects)
Listing 16.2.1.2 Subject Population (All Subjects)
Listing 16.2.1.3 Missing Visits Due to COVID-19 (All Enrolled Subjects)
Listing 16.2.1.4 Missing Assessments Due to COVID-19 (All Enrolled Subjects)
Listing 16.2.2.1 Major Protocol Deviations (All Enrolled Subjects)
Listing 16.2.3.1 Subject Inclusion and Exclusion Criteria Deviations (All Screened Subjects)

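### Multiple-dose concentration summaries pool full and renally reduced doses; add dose or renal group at the sampled interval as a by-variable

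*SAP*

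**What the plan says.** **Dosing.** Protocol 3.1 states: "The dose for the multiple-dose phase will be determined based on both body weight and renal function". Protocol Tables 5-2 and 5-3 give three levels below 34 kg (60, 45 and 30 mg/kg) and three at or above 34 kg (2000, 1500 and 1000 mg), all every 8 hours. Protocol 7.5.3.1.2 admits eGFR of 15 or more to this phase, and Protocol 5.2 lets the dose follow changes in renal function during treatment. Sampling falls in one interval between the 6th and 12th dose (Protocol 7.4).

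**Concentration summaries.** SAP 9.3.3 summarises concentrations "presented for plasma concentrations by cohort, phase (single-dose and multiple dose phases), infusion time (1, 2, and 3 hours), and nominal sampling time". The mean plot uses cohort, phase and infusion time, and Table 14.2.2 and Figure 14.2.3 carry these outputs. The individual plot in SAP 9.3.2 combines all subjects, one line each, with no dose or renal marking specified. Protocol 9.10 lists the same strata as SAP 9.3.3.

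**Parameters.** Protocol Section 2 names Cmax, AUC and half-life as endpoints of the primary PK objectives, in the multiple-dose phase "after a minimum of 4 doses". Under the lead-in "The following PK endpoints will be evaluated", SAP 9.2 lists one item, as does SAP 4.4: "Plasma cefiderocol concentrations".

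**The concern.** A mean over subjects on different doses and with different elimination rates estimates the exposure of no planned regimen. Reducing the dose as clearance falls tends to equalise AUC, but not the shape of the curve: slower elimination lifts the end of the interval relative to the peak. Late concentrations bear on time above MIC, the exposure measure on which Protocol 1.3 rests the dosing rationale. With a planned minimum of 10 subjects per cohort, one or two reduced-dose subjects can move the mean 8-hour value and inflate its SD, and the reader of the table could not tell why.

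The SAP already splits by infusion time, which is shortened only case by case with sponsor approval. Renal dosing is built into the design and has no such split. Baseline eGFR is not a full substitute, because the dose may have changed before sampling.

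**Working it through.** **Plan's own figures.** Four single-dose cohorts of 6 plus three multiple-dose cohorts of 10 give 24 + 30 = 54, the stated minimum. The dose fractions agree across weight bands: 45/60 = 1500/2000 = 0.75 and 30/60 = 1000/2000 = 0.50.

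**Inputs** (Protocol 1.2, adults)
- AUC ratio g to normal function (90% CI): mild 1.0 (0.8 to 1.3), moderate 1.5 (1.2 to 1.9), severe 2.5 (2.0 to 3.3).
- Half-life 2.4 h and AUC 386.1 µg·h/mL after 2000 mg over 3 h.

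**Step 1: AUC at the planned doses** is g × f, where f is the dose fraction.
- Moderate: 1.5 × 0.75 = 1.125.
- Severe: 2.5 × 0.50 = 1.25.

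**Step 2: steady-state concentrations.** One compartment, 3-h infusion every 8 h, volume unchanged by renal function.
- CL = 2000/386.1 = 5.18 L/h; k = ln 2/2.4 = 0.289 per h for normal function, and k/g in impairment.
- C(3) = [(dose/3)/CL] × (1 − e^(−3k))/(1 − e^(−8k)).
- C(8) = C(3) × e^(−5k).

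| | 3 h (µg/mL) | ratio | 8 h (µg/mL) | ratio |
|---|---|---|---|---|
| Normal, full dose | 82.8 | 1 | 19.5 | 1 |
| Moderate, 0.75 | 80.9 | 0.98 | 30.9 | 1.58 |
| Severe, 0.50 | 78.1 | 0.94 | 43.8 | 2.24 |

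**Step 3: range over the 90% CI of g.**
- 8-h ratio: moderate 1.07 to 2.28, severe 1.64 to 3.22.
- 3-h ratio: moderate 0.84 to 1.15, severe 0.80 to 1.18. Near-equality at 3 h therefore holds at the point estimates, not across the interval.

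**Step 4: effect on the mean 8-h value in a cohort of 10.**
- One severe: (9 + 2.24)/10 = 1.124, or +12%. The range is (9 + 1.64)/10 to (9 + 3.22)/10, or +6% to +22%.
- Three moderate: (7 + 3 × 1.58)/10 = 1.174, or +17%. The range is (7 + 3 × 1.07)/10 to (7 + 3 × 2.28)/10, or +2% to +38%.
- At the point estimates, assumed normal/moderate/severe mixes from 9/1/0 to 6/2/2 give +6% to +37% at 8 h and −0.2% to −1.6% at 3 h. The between-group CV at 8 h is 17% to 38%.

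**Model check.** The same model gives a single-dose Cmax of 74.6 µg/mL against the stated adult 89.7, which is 17% low (74.6/89.7 = 0.83). The ratios show direction and rough size only.

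**Single-dose phase.** Only normal or mild function enters, under one weight-based rule, and the adult mild-to-normal AUC ratio is 1.0. Pooling over renal dose levels does not arise there.

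**The case against.** The strongest reply is that Table 14.2.2 is descriptive and drives no decision. Exposure is confirmed in the single-dose phase before multiple dosing starts (Protocol 3.2). Progression rules sit in the PK analysis plan (Protocol 9.13, SAP 2.3), and dosing is confirmed by modelling and simulation (Protocol 1.3 and 5.3). Geometric mean, median, minimum and maximum are reported as well. Cefiderocol administration and eGFR are listed by subject, so dose and renal status can be traced. There may be few reduced-dose subjects, or none. All of this stands and limits the stakes. It does not make a mixed mean interpretable, and tracing subjects through listings is what a by-variable would spare the reader.

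A reader might also infer that the primary PK parameters have been dropped from the study. The documents do not show that. Protocol 9.1 places PK methods in both the SAP and a PK analysis plan, Protocol 7.7 says PK parameters are estimated with a population PK model, and SAP 2.1 and Section 9 send further PK work to separate planning and reporting. That plan is not available here. Pooling with other paediatric studies is described as part of that work, not all of it.

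Nor is SAP Section 12 shown to be false when it says "There were no changes from the analyses planned in the protocol". The concentration summary matches Protocol 9.10. Any mismatch lies between Protocol Section 2 and Protocol 9.10, and the SAP inherits it.

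**Conclusion.** The point holds for the multiple-dose phase, Cohorts 2 to 4, and only if subjects with moderate or severe impairment enrol or doses are reduced during treatment. In that case the pooled mean can misstate late concentrations: an 8-hour ratio of about 1.6 (1.1 to 2.3) for moderate and 2.2 (1.6 to 3.2) for severe impairment, and a shift of about 6% to 22% in a cohort mean from one severe subject in 10. The expected AUC difference is smaller, 12.5% and 25% at the point estimates.

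These sizes assume that adult AUC ratios apply to children, that volume does not change with renal function, and that one compartment is adequate. The renal mixes are also assumed. No view is taken on which dose is right.

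There is also a smaller gap in traceability. The SAP's delegation text names additional PK, population PK and PK/PD analyses, but not Cmax, AUC or half-life. From these two documents alone, the primary PK parameters cannot be followed to a planned output by cohort and phase.

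**What to change.** 1. In SAP 9.3.2, 9.3.3, Table 14.2.2 and Figure 14.2.3, keep the overall PKCS summary. For the multiple-dose phase, add dose level or renal group at the sampled interval as a by-variable, with reduced-dose subjects shown separately. Identify them in the individual plots and concentration listings. Define the group by the dose in force at sampling, not by baseline eGFR. Align Protocol 9.10 if it is next amended.
2. In SAP 4.4 and 9.2, state that the protocol's primary PK parameters (Cmax, AUC and half-life) are derived under the PK analysis plan and reported for this study by cohort and phase.

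The cost is SAP wording, one by-variable and a cross-reference. The downside is small subgroups, some of one or two subjects, for which individual values will say more than summary statistics. No subject needs to leave the PKCS population, and Section 12 needs no correction on this account.

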11.1. Extent of Exposure

Cefiderocol and SOC administration records will be listed chronologically by subject and study days.

Exposure duration and study drug regimen will be tabulated for the Safety Population. In addition, the total number of doses received for cefiderocol will be summarized.

The total number of doses will be calculated as the sum of each unique recorded infusion per subject.

Exposure duration in days will be calculated as (round up to an integer of (the stop date of the last dose/time (HH:MM) – the start date of the first dose/time (HH:MM) / (60*60*24))).

